11 PROCEDURES INVOLVED

A total of 20 ENDS users will be recruited for this study with equal numbers of men and women. All participants will be seen after an overnight abstinence of approximately 8 hours at Roswell Park Comprehensive Cancer Center (The Department of Health Behavior Human Exposure Lab) on 4 separate occasions, at least 5-7 days apart (with a maximum of 4 weeks between visits allowed before the participant is taken off study). Each study visit is expected to last approximately 2.0 to 2.5 hours. The anticipated duration of intervention is 4 weeks.

After 8-10 hour overnight product abstinence (confirmed by self-report and expired CO less than 8 ppm), participants will be admitted to The Department of Health Behavior Human Exposure Lab. This will be done so that effect of various e-liquid solutions on nicotine withdrawal symptoms might be assessed. (For analysis purposes, once the study is closed and the blood samples are analyzed, anyone with a nicotine concentration \leq 2 mL in their blood for the T0 sample will be deemed as adhering to the overnight abstinence. Anyone with a nicotine concentration $>$ 2 mL in their blood for the T0 sample will be marked as not adhering to the abstinence. Adjustments will be made for the analysis of this finding and controls set in place when running statistics on order to account for this finding.

Participants will be asked to take 20 puffs over 10 minutes (one puff every 30 sec) from the assigned ENDS product (Innokin EQs Ultra-Compact 2mL Refillable Pod Vaporizer equipped with a 800mAh battery and wattage set to 11.5W), presumed equivalent in nicotine yield to a single cigarette (based on pilot studies 20 puffs generate aerosol with cumulative nicotine yields from 1.5 mg to 1.7 mg). Participants will be video-recorded to analyze puffing behaviors (product operation, number of puffs, and time of puffing and exhaling vapors). Participants will also be asked to provide a urine sample before the 10 min puffing session as well as after the 10 min puffing session. Urine samples will be tested for cotinine, NNAL and VOC metabolites.

Venous blood samples to measure nicotine will be taken either through butterfly needle by a certified phlebotomist or through a catheter by a certified registered nurse before and 2, 4, 5, 6, 8, 10, 13, 15, 20, 30, 45, 60, 90, and 120 min after onset of use of ENDS product with tanks of each e-liquid solution. A total of 60 mL of blood may be collected using a 4mL green top heparinized vacutainer blood collection tube during each visit (15 collection time points, 4 mL at each time

Roswell Park Protocol No.: I 475819

point, not all collection time points will be fulfilled at each visit). If the participant is experiencing excessive blood clotting, the butterfly needle will be removed and a new butterfly needle will be inserted to continue with blood collection (the number of new butterfly needle insertions will never exceed three per study session). The butterfly needle or catheter may be placed in upper extremity or the hand of the participant. Nicotine in plasma will be measured by a high sensitivity GC-MS/MS method (4). Vital signs will be taken and expired CO will be measured before and 3 minutes after the use of each e-liquid solution (CO monitor, Bedfont, UK). Females of child-bearing potential will be asked to test urine for pregnancy.

At visit one only, participants will be asked to complete several questionnaires including: Demographics (**Appendix E**), Smoking History (**Appendix F**), Time-line Follow Back to assess past 30 day tobacco product use (5) (**Appendix G**), Penn State E-cigarette Dependence Index (**Appendix H**), and Taste Preference (**Appendix I**). During each visit participants will be asked to report on the Minnesota Nicotine Withdrawal Scale (MNWS) and the strength of nicotine withdrawal symptoms (craving, irritability, difficulty in concentration, and restlessness) before and after product use (**Appendix J**). Participants will also rate their mood before and after product use (**Appendix K**). Satisfaction with and helpfulness of the product will be measured at the end of each session using an adapted questionnaire (**Appendix L**). Acute subjective responses to the effects of nicotine will also be measured using the Drug Effect Questionnaire (DEQ-5) after product use (**Appendix M**) as well as a questionnaire to assess a participant's craving to smoke (**Appendix N**). Puffing topography will be assessed with an eTop monitor after all blood draws are complete. At this time, subjects will be asked to puff on the assigned ENDS product ad lib with the eTop monitor. Participants will also be asked to complete the product evaluation scale, which assesses subjective effects such as liking and satisfaction, at visit four after experiencing each e-liquid solution (**Appendix O**). Additionally, participants will complete the Experimental Tobacco Marketplace product purchasing task (**Appendix P**). During the ETM, participants will purchase hypothetical tobacco products in an online store analog with an account balance determined by past 30 day-tobacco product use at Session 1. The product being sampled during the session will be available for purchase under four different price conditions. Other tobacco products will be simultaneously available at a constant price. Average time to completion using four price conditions is 8 minutes. Participants will also be asked to answer a series of questions regarding involving Sensory Measures (**Appendix Q**).

Table 3. Schedule of Procedures and Observations

Visit	#1	#2	#3	#4
Week	1	2	3	4
Nicotine Solution	E-liquid Solution #1	E-liquid Solution #2	E-liquid Solution #3	E-liquid Solution #4
Informed Consent ¹	X			
Demographics and Smoking history (Appendix E) Timeline Follow-Back (Appendix G) Penn State E-Cigarette Dependence Index (Appendix H) Taste Preference (Appendix I), ENDS Dependence Scale (Appendix R)	X			
Vital signs	X	X	X	X
Blood Draw for Analytical Testing ²	X	X	X	X
Pregnancy Test (Urine)	X	X	X	X
Urine Sample (before and after 10min puffing session)	X	X	X	X
Puffing Topography	X	X	X	X
CO Pre and Post-Product Use ³	X	X	X	X
Minnesota Nicotine Withdrawal Scale (MNWS)(adapted) (Appendix J) Pre and Post Product Use	X	X	X	X
Positive Negative Affect Scale (PANAS) (Appendix K) Pre and Post Product Use	X	X	X	X
Satisfaction With and Helpfulness of the Products (Appendix L) Post Product Use	X	X	X	X
Drug Effect Questionnaire (DEQ-5) (Appendix M) Post Product Use	X	X	X	X
Modified Questionnaire of Smoking Urges (QSU-brief) (Appendix N) Post Product Use	X	X	X	X
Adverse Events	X	X	X	X
Concomitant Medications	X	X	X	X
Product Satisfaction Scale (Appendix O) Post Product Use				X
Experimental Tobacco Marketplace (ETM) (Appendix P)	X	X	X	X
Sensory Measures (Appendix Q) Post Product Use & Delay Discounting Task	X	X	X	X

1 Must be signed prior to any study related assessments or procedures.

2 See **Section 15** for Data and Specimen Banking

3 Expired CO will be measured before, and 3 minutes after the use of each product

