5 LOCAL AND STUDY-WIDE RECRUITMENT METHODS

Participants will be recruited from advertisements in local newspapers/magazines, posters, community centers, churches, and from several websites (Roswell websites, Craigslist.org, Facebook, and Instagram). An example of the participant recruitment material can be found in **Appendix C**. Applicants will be invited to call a local number. On calling, applicants will be given a brief explanation of the study and their eligibility to participate will be assessed (**Appendix D**). Those who meet eligibility criteria will be included in the study and attend 4 weekly sessions. We anticipate that each session will take 120 minutes. After completion of each visit, participants will be asked to vape as usual over the next week, and the procedures will be repeated every week for the total of 4 visits.

Study participants will be compensated by cash for each study visit completed and will receive additional "bonus" cash if all study visits have been completed. Payments will be disbursed according to the following schedule (**Table 1**):

Table 1 Study Payment Schedule

Study Visit	Payment Amount
1	\$50.00
2	\$60.00
3	\$70.00
4	\$80.00
All Visits Completed	\$90.00 bonus
TOTAL	\$350.00

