8 STUDY ENDPOINTS

8.1 Primary Endpoint(s)

- Maximum concentration of nicotine in plasma (C_{max}), the area under the concentration – time curve from 0 to 120 min (AUC), and the time to maximum concentration (T_{max}).

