15 DATA AND SPECIMEN BANKING

Pharmacokinetic Blood Sample Collection

Whole blood samples for analytical testing of nicotine and cotinine levels will be collected via venipuncture using a butterfly needle or a venous catheter using 4 mL green-top heparinized collection tubes. The blood will be drawn by either a certified study phlebotomist using a butterfly needle, or a venous catheter placed by a registered nurse. Blood sample collection will be obtained at each study visit prior to and 2, 4, 5, 6, 8, 10, 13, 15, 20, 30, 45, 60, 90, and 120 min after onset of use of each nicotine solution, approximately 4 mL will be taken at each time point (not all collection time points will be fulfilled at each study visit). If the participant is experiencing excessive blood clotting, the butterfly needle will be removed and a new butterfly needle will be inserted to continue with blood collection (the number of new butterfly needle insertions will never exceed three per study visit). The butterfly needle or venous catheter may be placed in the upper extremity or in the hand of the participant.

For all participants, the amounts drawn will not exceed 240 mL for the entire study and collection will not occur more frequently than 2 times per week.

Urine Sample Collection

Urine samples will be taken before and after ENDS product use. Female urine samples will be tested for pregnancy.

All blood and urine samples will be immediately transported to the Health Behavior Department Laboratory (Roswell Park Comprehensive Cancer Center); the blood samples will be centrifuged to separate the plasma from whole blood. The plasma will be aliquoted into cryovials that are labeled with the participant's initials, participant's study number, clinical study number, protocol time point, product, and protocol day. Urine samples will be transferred to 15 mL Flacon tubes. The samples will immediately be frozen at -70°C or below in [name] until analyzed. Plasma will be analyzed for cotinine and nicotine using UPLC-MS/MS method (6). Urine samples will be tested for cotinine, NNAL and VOC metabolites. Female urine samples will be tested for pregnancy. All blood and urine sample results are recorded in logs and kept in:

[name]
Gratwick Basic Science Building (GBSB)
Health Behavior Department Laboratory
Laboratory location: 4th Floor, Room 4942
Laboratory [contact]
[name] office number: [contact]

Roswell Park Protocol No.: I 475819

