19.4 Primary Analysis

The primary objective is to evaluate whether AUC nicotine, C_{max} or T_{max} differ between free-base and salt-based versions of the same liquid, controlling for flavoring and nominal nicotine concentration.

Each outcome will be modeled as a function of base (free-base versus salt-based), flavor (tobacco versus unflavored), their interaction, prior combination indicator (for carry-over effect), and a random subject effect using a linear mixed model. All model assumptions will be verified graphically and transformations will be applied as appropriate. The effect of “base” on the AUC nicotine, C_{max} and T_{max} measures will be evaluated using tests about the least square means of “base”. Additionally, 95% confidence intervals about the mean differences will be obtained.

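### Pre-use (T0) nicotine is reduced to a yes/no flag with an undefined adjustment, and the 19.4 model has no T0 term; pre-specify visit-level continuous T0 for AUC and Cmax

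*Combined protocol and SAP*

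**What the plan says.** Section 11 sets the adherence rule. A T0 above "2 mL in their blood for the T0 sample will be marked as not adhering to the abstinence", and one at or below it counts as adherent. The classification is made "once the study is closed and the blood samples are analyzed". The text then says "Adjustments will be made for the analysis of this finding and controls set in place when running statistics". No covariate, exclusion, baseline correction or sensitivity analysis is named. The rule speaks of anyone with such a value, so it could apply to a person or to a visit, and mL is not a unit of concentration.

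Section 19.4 lists the primary model terms: base, flavor, their interaction, a "prior combination indicator (for carry-over effect), and a random subject effect using a linear mixed model". T0 and the flag appear nowhere in section 19. The primary endpoints in 8.1 are Cmax, Tmax and the "curve from 0 to 120 min (AUC"), with no baseline correction stated.

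Two other places bear on this. Section 5 says that between visits "participants will be asked to vape as usual over the next week". Sections 11 and 15 both expect missed draws ("not all collection time points will be fulfilled at each visit"; "not all collection time points will be fulfilled at each study visit"), and no rule covers a visit without T0.

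**The concern.** Section 11 promises an adjustment that the statistical plan does not contain. Nicotine already in the blood at T0 adds directly to AUC over 120 minutes and to Cmax.

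The existing terms cover only part of this. The random subject effect absorbs a person's stable T0 level but not visit-to-visit variation. The prior-combination term describes the last study liquid, not own-product use. A flag would discard the size of T0 on both sides of the cut-off: values of 2.1 and 15 are treated alike, and a value of 2 is treated as zero.

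Two things are at stake: some precision in the salt contrast, and a primary-model choice that can still be made with outcomes in hand. The second does not depend on T0 varying much.

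**Working it through.** **The plan's own figure.** Section 19.1 gives a difference of 700, SD 500, two-sided 0.05, 80% power and n = 18. Per group, n = 2 × (1.96 + 0.84)² × (500/700)² ≈ 8.0. The noncentral-t power is 74.0% at 8 per group and 79.6% at 9, so 18 reproduces as 9 + 9 independent observations.

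**What T0 adds to AUC.** The documents give no half-life or T0 distribution, so both are assumed, and the cut-off is read as ng/mL. With k = ln 2 / half-life, the added AUC is T0 × (1 − exp(−120k))/k:
- 60-min half-life: 64.9 per 1 ng/mL
- 180-min half-life: 96.1 per 1 ng/mL
- no decay (outer limit): 120 per 1 ng/mL

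So T0 = 2, which counts as adherent, adds 130 to 192 ng/mL × min over half-lives of 60 to 180 min.

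**Effect on the salt contrast.** The design was simulated under the null, 8,000 runs per case: 20 people, Williams order, the 19.4 fixed terms with subject effects, and residual SD 500 apart from T0. T0 was gamma with mean equal to SD, all of it varying within person, and the flag was set per visit. Standard errors at multipliers 64.9 and 120:

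| T0 SD (ng/mL) | Visits above 2 | No T0 term | Flag | Continuous T0 |
|---|---|---|---|---|
| 1 | 14% | 118.0, 120.4 | 118.5, 119.5 | 118.2, 118.2 |
| 2 | 37% | 121.0, 130.2 | 119.6, 123.3 | 118.2, 118.2 |
| 3 | 51% | 125.8, 144.9 | 122.1, 132.4 | 118.2, 118.2 |

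The mean contrast was within 3 of zero in every case.

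**Gain over the flag with realistic decay.**
- 60 min: SD 2, 1 − 118.2/119.6 = 1.2%; SD 3, 1 − 118.2/122.1 = 3.2%.
- 180 min, scaling the flag model's excess variance by (96.1/64.9)² = 2.19: SD 3, 122.1² − 118.2² = 937, × 2.19 = 2,055, so SE = √(13,971 + 2,055) = 126.6 and the gain is 6.6%. The same steps at SD 2 give 2.5%.
- Half of the T0 variance between people, multipliers 65 to 96: 0 to 2% at SD 2 and 2 to 4% at SD 3.

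About 0 to 6% is therefore a fair summary, with one corner slightly above.

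**Sensitivity to how 500 is read.** If 500 is the total within-person SD, T0 noise included (lognormal T0, 120-min half-life), the flag and continuous SEs are 117 and 115, 114 and 107, and 114 and 91 at median T0 of 1, 2 and 3. The gain is then larger when T0 is high.

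**Power for 700.** At the worst SE in the table, 700/144.9 = 4.83, and Φ(4.83 − 1.96) = 0.998.

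**Open choice.** Each method fixed in advance has type I error of 4.9 to 5.3%. If the smaller p of flag and continuous T0 were always reported, it would be about 5 to 8%.

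**Cmax.** With the peak near 10 min, T0 adds contrast noise of SD_T0 × (0.89 to 1.00) × √(2/40): 0.20–0.22, 0.40–0.45 and 0.60–0.67 ng/mL at SD 1, 2 and 3. No Cmax SD is given, so no relative gain can be stated.

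**Missed T0.** At an assumed 10% missing, dropping those visits gives SE 129. Keeping them with mean T0 and a missing indicator gives 120 to 122. At 5% the figures are 123 against 119 to 121.

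**The case against.** Several points on the other side stand:
- The trial is a pilot, randomized order protects the comparison, and the planned power is not in danger.
- The larger gains need slow decay, high T0 variation that is mostly within person, and a sample in which about half the visits break abstinence. At SD 1 there is nothing to gain.
- The documents say that some time points may be missed, not that T0 will be. The missing rates above are invented, and SE 129 arises only if a T0 term is fitted on complete cases, which the plan does not propose.
- Section 11 ties the abstinence rule to assessing withdrawal symptoms. A fix limited to AUC and Cmax would strip a promised safeguard from withdrawal relief (8.2, 19.5) and leave Tmax unaddressed. The fix must therefore cover both.
- Section 19.4 allows transformations, so the scale of T0 has to be stated too.

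A reader might also infer more than the text supports:
- That the definition of the adjustment is deferred until the study closes. Only the classification is tied to closure; the adjustment is simply never defined.
- That leaving T0 unadjusted is one of the options, which would put the type I bound at 6.1 to 8.9%. Section 11 commits to some adjustment, so flag versus continuous T0 is the fairer pair.
- That salt versus free-base is biased. Neither the design nor the simulation supports this.

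What remains is that a promised adjustment is undefined and absent from 19.4, and that a better use of an already planned measurement is available.

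**Conclusion.** The point holds as a low-cost improvement that should be made; it is not a threat to the trial's main comparison. Compared with the flag, continuous visit-level T0 gives no useful precision at a T0 SD of 1 ng/mL and about 0 to 6% in standard error at SD 2 to 3. It also removes a model choice worth at most about 5 to 8% type I error instead of 5%; this is an upper bound, not a prediction.

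These sizes rest on assumed T0 distributions, half-lives of 60 to 180 min, the cut-off read as ng/mL, and 500 taken as residual SD apart from T0. The gaps in the text do not depend on those assumptions: the adjustment is undefined, 19.4 has no T0 term, the flag's level and unit are unclear, and no rule covers a missed T0.

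**What to change.** In 19.4:
- Add visit-specific T0 as a continuous covariate in the AUC and Cmax models, on the same scale as the outcome if that is transformed.
- State a rule for T0 values below the assay limit.
- Keep all visits in the analysis, whatever their flag.
- If T0 was not drawn, keep the visit, set T0 to the mean of the observed values and add a missing-T0 indicator. T0 precedes product use under blinding, so its absence is not caused by the liquid. The same value can serve as the time-0 point of AUC, where its trapezoidal weight is only 1 minute of 120 (next sample at 2 min).

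In section 11:
- Give the cut-off in a concentration unit and apply the flag per visit.
- Replace the open sentence on adjustments. For AUC and Cmax, the flag is used only in a sensitivity refit of 19.4, in place of continuous T0.
- Retain the adherence adjustment elsewhere by naming one covariate in advance, the per-visit flag or continuous T0, for Tmax and for the withdrawal-relief models in 19.5.

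The cost is one degree of freedom per model, two if any T0 is missing, plus SAP wording. The T0 draw is already planned at every visit.

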1 OBJECTIVES

- To determine the effect of nicotine salt (nicotine benzoate) and free-base nicotine in different flavored e-liquid solutions on puffing behaviors and systemic exposure to nicotine from ENDS by 1) Assessing short-term effects on nicotine cravings, withdrawal, and satisfaction from single use of ENDS refilled with flavored nicotine salt or flavored free-base nicotine solutions with two different flavors (tobacco or unflavored) in current daily ENDS users following an overnight fast; and 2) Comparing users' perceptions and preferences towards inhaling vapors containing nicotine salt (nicotine benzoate) or free-base nicotine with two different flavors (tobacco and unflavored) versus their regular brand.
- This project provides important information on whether the pharmacokinetics of nicotine delivery differ between salt and free-base forms of e-liquid of equivalent nominal concentration using the same device, and whether the previously observed effects of flavors on subjective effects differ between salt and free-base forms.

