8.2 Secondary Endpoint(s)

- Perceived harshness, satisfaction, liking, and relief of nicotine withdrawal symptoms.

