Appendix J
Minnesota Tobacco Withdrawal Scale

How are you feeling at this very moment? Please mark an (X) in ONE box for each condition					
	Not at all	Slightly	Somewhat	Very	Extremely
Depressed					
Irritable					
Anxious, nervous					
Restless					
Dizziness					
Hungry					
Nausea					
Poor concentration					

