Appendix N

Modified Questionnaire of Smoking Urges (QSU-breif)

Please answer each statement below on a scale from 0 (Strongly Disagree) to 100 (Strongly Agree)

1. I have a desire for my regular device and e-liquid right now. _____
2. Nothing would be better than using my regular device and e-liquid right now. _____
3. If it were possible, I would probably use my regular device and e-liquid right now. _____
4. I could control things better right now if I could use my regular device and e-liquid right now. _____
5. All I want right now is my regular device and e-liquid right now. _____
6. I have an urge for my regular device and e-liquid right now. _____
7. My regular device and e-liquid would taste good right now. _____
8. I would do almost anything for my regular device and e-liquid right now. _____
9. Using my regular device and e-liquid would make me less depressed. _____
10. I am going to use my regular device and e-liquid as soon as possible. _____

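### Section 11 promises craving ratings before and after product use, but the cited form has no craving item and the urges scale is scheduled after use only

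*Combined protocol and SAP*

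**What the plan says.** Section 1 gives as its first aim "Assessing short-term effects on nicotine cravings, withdrawal, and satisfaction from single use of ENDS". The secondary endpoints in Section 8.2 are "Perceived harshness, satisfaction, liking, and relief of nicotine withdrawal symptoms"; craving is not named there, nor among the outcomes of Section 19.5.

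Section 11 says that at each visit participants report "the strength of nicotine withdrawal symptoms (craving, irritability, difficulty in concentration, and restlessness) before and after product use", and it cites Appendix J for this. Table 3 agrees on the timing of that form: "Minnesota Nicotine Withdrawal Scale (MNWS)(adapted) (Appendix J) Pre and Post Product Use". Appendix J opens with "How are you feeling at this very moment" and then lists its symptoms.

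The urges questionnaire is a separate form, Appendix N. Table 3 lists it as "Modified Questionnaire of Smoking Urges (QSU-brief) (Appendix N) Post Product Use". The text of Section 11 mentions it in the same sentence as the Drug Effect Questionnaire, which is given after use.

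Section 9 describes timing differently. It places the subjective measures at the same times as the blood draws, which include one draw before use. The list that follows is introduced as non-exhaustive and does not include the urges questionnaire.

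**The concern.** The text and the forms disagree about craving. Section 11 counts craving among the withdrawal symptoms to be rated twice per session, but the form it cites does not ask about it, and the form that does ask is given once, after use. A site that follows Table 3 and the printed appendices will therefore hold no craving score from the abstinent state.

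Two things are at stake. First, the fall in craving from before to after a single use cannot be calculated for any liquid. Section 11 asks for overnight abstinence so that effects on withdrawal symptoms can be assessed, and craving in that state goes unrecorded. Second, there is no same-visit pre-use craving score to use as a covariate, so visit-to-visit variation in starting craving stays in the residual of any analysis of post-use urges. Neither can be recovered once a visit is over.

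**Working it through.** The plan states no figure on this point, so the check is to set each form's timing against its content.

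| Form | Timing | Momentary craving or urge content |
|---|---|---|
| Appendix J, withdrawal scale | Before and after, every visit (Table 3) | None of 8 items: depressed, irritable, anxious or nervous, restless, dizziness, hungry, nausea, poor concentration |
| Appendix K, affect scale ("Positive Negative Affect Scale (PANAS) (Appendix K) Pre and Post Product Use") | Before and after, every visit | None of 20 words |
| Appendix N, urges questionnaire | After, every visit | All 10 items, for example "I have an urge for my regular device and e-liquid right now" |
| Appendix M, drug effects | After in Table 3 and Section 11 | One item on wanting more nicotine |
| Appendix L, satisfaction | After, every visit | Items 3 and 9: recalled amount and speed of urge relief |
| Appendix H, dependence index | Visit 1 only | Urges over the past week, not the present state |
| Appendix Q, sensory measures | After, every visit | One item on how craving generally behaves, not the present state |

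**Step 1.** Section 11 names four symptoms: craving, irritability, poor concentration and restlessness. Appendix J has the last three and lacks the first.

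**Step 2.** Table 3 labels two forms as pre-use at every visit, J and K. Craving items on them: 0 of 8 and 0 of 20.

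**Step 3.** Section 9 does not settle the matter. Read literally, its blood-draw timing would include a pre-use rating, but it does not name Appendix N. It does name the drug effects scale, which Table 3 places after use and whose own instructions refer to feelings following use of the product. It also names the ENDS dependence scale, which Table 3 gives at visit 1 only. Section 9 and Table 3 therefore conflict on timing more widely.

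**Step 4. Illustrative size.** The documents give no correlation between pre-use and post-use craving, so ρ, the within-subject correlation of the two scores across visits, is an assumption. Take equal pre-use and post-use variances and set the residual variance of the post-use score to 1. With the pre-use score as covariate the variance is 1 − ρ². For the raw change score it is 2(1 − ρ).

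| Assumed ρ | Variance with covariate, 1 − ρ² | Variance removed | Reduction in standard error, 1 − √(1 − ρ²) | Variance of change score, 2(1 − ρ) |
|---|---|---|---|---|
| 0.3 | 0.91 | 9% | about 5% | 1.4 |
| 0.5 | 0.75 | 25% | about 13% | 1.0 |
| 0.7 | 0.51 | 49% | about 29% | 0.6 |

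The covariate never does worse than the unadjusted post-use score, apart from the small cost of estimating one slope. The change score is less precise than the post-use score when ρ is below 0.5, and less precise than the covariate analysis in every row.

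**The case against.** The strongest reply has four parts.

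- **Craving is not a named endpoint.** It is in the Section 1 aim but not in the primary objectives, Section 8 or the Section 19.5 outcomes. It reaches the secondary endpoint only because Section 11 counts it among the withdrawal symptoms. This stands, and it keeps the point modest.
- **The comparison of interest is between liquids.** A reader might infer that post-use urges are biased by differences in pre-use craving, for instance after imperfect abstinence. The documents do not support that. Each participant uses all four liquids in an order randomised by a Williams design, so such differences add noise rather than bias.
- **Other data bear on it.** A reader might also infer that craving relief goes unmeasured. It does not: Appendix L asks at every visit how much and how fast the urge was relieved, and the answers to item 9 are not scored against the regular device. Pre-use withdrawal and affect scores are taken, and Section 11 says that abstinence failures found in the pre-use blood sample will be adjusted for. All this stands. Still, recalled relief is not a measured baseline, and none of the other data is a pre-use craving score.
- **The text does order the measurement.** Section 11 requires craving before use, and Section 9 may imply pre-use ratings. It would therefore go too far to say that the plan intends no pre-use craving measure, or that none will be taken: the form in use may differ from the printed appendix. What the documents show is a conflict between Sections 9 and 11, Table 3 and Appendix J.

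A single craving item added to Appendix J would also meet the letter of Section 11. It would not give a pre-use score on the same scale as the post-use urges questionnaire.

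**Conclusion.** The point holds as an inconsistency with a limited consequence. Under Table 3 and the forms as printed, no visit yields a pre-use craving score, so the before/after comparison in Section 11 cannot be made and there is no same-visit craving covariate. This conclusion rests on the documents alone.

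The loss is the change from the abstinent state plus some precision. The precision figures (9%, 25% and 49% of residual variance) depend wholly on assumed correlations and show scale only. The randomised comparison of post-use urges stays valid, so the documents do not support concluding that the craving aim in Section 1 is unanswerable. The point ranks as a cheap improvement.

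**What to change.** 1. In Table 3 and Section 11, schedule Appendix N before and after product use at all four visits. Its items ask about the present moment and the participant's regular device, so they can be used unchanged before the session.
2. In Section 11, attribute craving to Appendix N, and leave Appendix J for the symptoms it contains. If the form in use already has a craving item, correct the printed Appendix J to show it.
3. Align the timing statement in Section 9 with Table 3, naming which forms are given at which times.
4. In Section 19.5, state the role of craving. Analyse post-use urges with the planned mixed model plus the same-visit pre-use score as covariate. Give the raw change descriptively only, since it loses precision when the correlation is below 0.5.

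The cost is ten extra self-report items per visit, or 10 × 4 = 40 per participant, at an assumed one to two minutes per visit, and a second copy of an existing data-capture form. No staff or procedures are added. The change helps only visits not yet completed.
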